**7) Pyridium 100-300mg/day**

8) Microbiome: Methenamine

9) Vaginal estrogen

At least once within 12 weeks of initial visit:

10) Intravesical evaluation: Cystoscopy to evaluate for hunner ulcers or variant (treat with Kenalog injection alone if Hunner ulcers or variant with or without hydrodistention if no hunner ulcers)

11) Bladder instillations x 6 weeks (lidocaine, heparin, sodium bicarb, available glucocorticoid (dexamethasone, etc), gentamicin)

-Invasive interventions to be repeated as needed per patient.

Data will be stored and managed in a RedCap database

**Measures to reduce loss to follow up:**

Phone calls and email from study coordinators.

**Potential confounding variables:** patients frequently have overlapping pain syndromes; likely many different CPP phenotypes. Patients will be enrolled sequentially.

**Demographic data:**

Age, self-identified race, BMI, menopausal status, past medical history, past surgical history, psychiatric history, tobacco, sexual assault/abuse history, history of prior interventions for their chronic pain condition, internal vs. external referral

**Study Size/Power Calculation:** based on the primary outcome, the primary outcomes is defined as the change in the total OLS score from baseline to 12 weeks compared between the groups. Based on previous studies, patients with IC/BPS have a baseline OLS score following standard medical treatment of  $24 \pm 5.6$  190 points. . A 4.03-point

decrease from baseline on the OLS-ICSI corresponds with at least a 50% perceived improvement in symptoms, we have chosen to use 6 points, to represent 75% improvement. We desired 90% power to detect a 6-point or larger difference in the mean score change between the groups with a 2-sided t-test at a significance level of  $\alpha=0.05$ . Accounting for 20% dropout, the target sample size was 40 for each group (80 total).

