#### **Definition of outcome measure and method of ascertainment:**

Data collected at baseline, 6 weeks, 12 weeks, 6 months, 1 year

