#### Primary Outcome

--O'Leary Sant Questionnaire (OLS), comprised of Interstitial Cystitis Symptom Index (ICSI) and Problem Index (ICPI), at 12 weeks from baseline  
MCID: 4 points for ICSI

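### The only test the plan names is an unadjusted t-test on change in total OLS; it is valid but inefficient, and adjusting for baseline OLS (preferably in a repeated-measures model) would be more precise at no patient cost

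*Combined protocol and SAP*

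**What the plan says.** The Primary Outcome section names the O'Leary Sant questionnaire, "comprised of Interstitial Cystitis Symptom Index (ICSI) and Problem Index (ICPI), at 12 weeks from baseline", without a method of analysis. The Study Size/Power Calculation text makes the endpoint more specific: it is "defined as the change in the total OLS score from baseline to 12 weeks compared between the groups". The same text gives the only statistical test in the document: "We desired 90% power to detect a 6-point or larger difference", where that difference is the "difference in the mean score change between the groups with a 2-sided t-test". The significance level is 0.05, 20% dropout is allowed for, and the target is 40 women per arm.

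The section on outcome measures and their ascertainment sets the visit schedule: "Data collected at baseline, 6 weeks, 12 weeks, 6 months, 1 year". A 6-week OLS will therefore exist for most women, but no role for it in the primary comparison is described. The document states no covariates, analysis set or missing-data rule. The passage on loss to follow-up lists only contacts by telephone and email.

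**The concern.** A t-test on change scores subtracts the whole of each woman's baseline score. Unless baseline and 12-week scores are perfectly correlated, this over-corrects: women with high baseline scores tend to improve more whatever their arm, and that regression to the mean stays in the comparison as noise. Estimating the baseline coefficient from the data removes it.

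This matters here for two reasons. The trial is small, with about 32 evaluable women per arm after the dropout allowance. Baseline OLS may also vary widely, because women can enter either on an OLS threshold or on levator spasm, and no stratified randomisation is described. A chance baseline difference between arms is therefore a practical possibility.

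The second issue is missing 12-week scores. A change-score t-test has nothing to compute for a woman without one. Her 6-week score would go unused, and the assumption made about her would be left implicit.

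**Working it through.** **Inputs from the Study Size/Power Calculation.** Difference 6 points, SD 5.6 (attached to an OLS score of 24, not to a change), two-sided alpha 0.05, power 90%, dropout 20%, 40 per arm, hence 40 × 0.8 = 32 evaluable per arm.

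**Assumed, not in the documents.** The baseline to 12-week correlation r, taken as 0.3 to 0.7, and the 6-week to 12-week correlation given baseline, q, also 0.3 to 0.7.

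**1. The plan's own figure.** With difference 6, SD 5.6 and 90% power, an exact t calculation needs 20 per arm, and 20/0.8 = 25, not 40. With an SD of change of 5.6 × √2 = 7.92 (r = 0) it needs 38, and 38/0.8 = 47.5, so 48. Forty per arm corresponds to an SD of change of about 7.29. The target therefore does not follow from the stated inputs. That is a separate point, but it means the SD of change is uncertain, so several values are carried below.

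**2. Variance.** With equal variance σ² at baseline and 12 weeks:
- change score: 2σ²(1 − r)
- baseline-adjusted: σ²(1 − r²)
- ratio: (1 − r²)/[2(1 − r)] = (1 + r)/2

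If the two SDs differ (σ₁ at baseline, σ₂ at 12 weeks), the change-score variance exceeds the adjusted variance by (σ₁ − rσ₂)², which is never negative. Apart from the one degree of freedom spent on the covariate, adjustment does not lose.

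**3. Size at the planned 6 points, 32 per arm, single-time SD 5.6.** Standard error = SD × √(2/32).

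| r | SD of change | Adjusted SD | Variance ratio | SE, change → adjusted | Power, change → adjusted |
|---|---|---|---|---|---|
| 0.3 | 6.63 | 5.34 | 0.65 | 1.66 → 1.34 | 94.6% → 99.3% |
| 0.5 | 5.60 | 4.85 | 0.75 | 1.40 → 1.21 | 98.8% → 99.8% |
| 0.7 | 4.34 | 4.00 | 0.85 | 1.08 → 1.00 | over 99.9% for both |

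Confidence intervals narrow by 1 − √ratio: 19%, 13% and 8%. Equivalently, 32 × (1 + r)/2 = 20.8, 24.0 and 27.2 women per arm with adjustment match 32 without it.

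**4. Sensitivity to the SD.** If the SD of change is about 7.29, power at 6 points rises from 90% to about 98%, 96% and 94% at r = 0.3, 0.5 and 0.7. If the SD of change is itself 5.6, power is already 98.8% and rises above 99%. If r = 0 and the single-time SD is 5.6, the t-test has 84.7%.

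**5. What the 6-week score adds.** Suppose 40 per arm are randomised, n₆ are seen at week 6 and 32 at week 12, with monotone dropout. The variance relative to adjusted completers is (1 − q²) + q² × 32/n₆. At n₆ = 34 and q = 0.3 this is 0.91 + 0.09 × 32/34 = 0.995. At n₆ = 40 and q = 0.7 it is 0.51 + 0.49 × 32/40 = 0.902. The gain is therefore 0.5% to 10% of variance, and zero if no 12-week score is missing.

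**6. Differential dropout (illustrative).** Simulations used 40 per arm, correlations of 0.5 (baseline with each visit) and 0.7 (week 6 with week 12), and an assumed 10% versus 30% dropout driven by the 6-week score. The completer t-test was off by 0.13 to 0.25 points with SE 1.42. Completer ANCOVA was off by 0.33 with SE 1.23. A baseline-adjusted likelihood analysis including week 6 was off by about 0.02 with SE 1.20 to 1.21. The largest error, 0.33, is 5.5% of the 6-point target.

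**The case against.** The strongest reply is that the t-test appears only in the sizing text, so it may be no more than a planning device. That is formally correct. However, the endpoint is itself defined as a change compared between arms, and no other test is named. Either the t-test is the default analysis or no primary analysis is specified, and the remedy is the same in both cases.

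Several stronger readings are tempting, and the documents do not support them.

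- *The plan discards the baseline.* It does not. A change score uses the baseline, but with a coefficient fixed at 1.
- *The plan restricts the analysis to women with a 12-week score.* No such rule is written. It follows only if the t-test is applied without imputation.
- *The trial is underpowered without adjustment.* At 6 points and r from 0.3 to 0.7 with a single-time SD of 5.6, the t-test already exceeds its 90% target. At 4.03 points power would go from 67% to 84% at r = 0.3, but the protocol gives 4.03 as a patient's own decrease on the ICSI, one component of the total. It is not a difference between arms in total OLS.
- *Dropout will differ by arm and bias the result.* One arm moves to another site and treatment is not blinded, so this is plausible. The plan states only a single 20%, however, and the simulated bias is a fraction of one standard error.

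It also stands that, given randomisation, a change-score t-test is a valid comparison. The issue is efficiency, together with conditional bias when baselines happen to differ.

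**Conclusion.** The point holds as one of efficiency and specification, and the change is worth making. Baseline adjustment lowers variance by 35%, 25% or 15% at r = 0.3, 0.5 or 0.7, with r assumed. Because power at 6 points is already high under most readings of the SD, the practical return is a narrower interval and a margin if the true difference is below 6 or the SD above 5.6. That margin has some value, since the target of 40 per arm cannot be reproduced from the stated inputs.

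Nearly all of the precision gain comes from the baseline covariate. The repeated-measures form earns its place mainly by letting women with a 6-week but no 12-week score contribute under an explicit missing-at-random assumption. Bias from unequal dropout remains speculative and was small in the scenarios examined.

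**What to change.** Add a short statistical analysis section, before any comparison by arm, that names a baseline-adjusted primary analysis: 12-week total OLS compared between assigned arms with baseline OLS as a covariate.

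Preferably fit it as a repeated-measures model of OLS at 6 weeks, 12 weeks, 6 months and 1 year. Include arm, visit, arm-by-visit, baseline OLS and baseline-by-visit, in all randomised women with any post-baseline score, analysed as assigned. Declare the 12-week arm contrast primary, and state the missing-at-random assumption. If the repeated-measures model is not wanted, ANCOVA at 12 weeks is the minimum; it secures most of the precision but does not deal with missing 12-week scores, so a missing-data rule must accompany it.

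The cost is analysis-plan wording and slightly more analysis work. No additional data, visits or patients are needed.

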### **Ethical Concerns:**

Pain patients are a vulnerable population.

**Strengths/Weaknesses;** patients cannot be blindly randomized, interventions are evidence-based but not being studied separately. There are likely differing phenotypes of pain patients (endometriosis vs. infectious vs. trauma) making for a heterogeneous population.

**Timeline:** 12 month enrollment and 12 month follow up.

### **Budget:**

Research Manager (1-2 years)-\$10K

Research Operations Coordinator (1-2 years) \$25K

Data Collection Tools (RedCap, database management, tablets for surveys, statistics, analytics)-\$5K

Patient Incentives: 5 time points

\$25 for each first 4 visits, \$50 for final visit (\$12K)

Promotional Materials/Design/Publicity -\$1K

General Materials (Office supplies including file folders, printing supplies)\$1K

Mail supplies (postage)\$1K

Estimated Total: \$50K

